12.2.3.7 The ability to detect change (responsiveness)

The ability to detect change (responsiveness) will be analyzed by calculating the effect size (ES), defined as the mean change over time divided by the standard deviation at baseline.

The ES will be estimated as $ES = \frac{\bar{y}}{sd_{x_1}}$, where $y_i = x_{i2} - x_{i1}$ and x_{i1} = domain intensity over

baseline for patient i , x_{i2} = domain intensity over the treatment period for patient i , and sd_{x_1} = standard deviation of the domain intensity over baseline.

The ES will be presented graphically, by collapsed improvement/deterioration OTE-categories (Table 4).

Data from patients with available data for both terms in the change calculation ($x_{i1} - x_{i2}$) will be used when calculating the SD at baseline.

12.2.3.8 Responder definition

The proposed values, which form the responder definitions (both the responder definition and the alternative responder definition originally derived in study [D9120C00027](#)), based upon clinically meaningful change, will be evaluated by graphical depiction of the intra-patient change in proportion of days of not more than mild symptoms from baseline to the entire treatment period, versus the cumulative proportion of patients achieving that change for each of the collapsed OTE categories unchanged, small improvement, moderate improvement and large improvement, as assessed at the visit after 4 weeks treatment (visit 6) or at early discontinuation.

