4.1 Inclusion criteria

For inclusion in the study patients should fulfil the following criteria:

1. Provision of informed consent prior to any study specific procedures
2. Male or female. Females of childbearing potential must be using a highly effective contraceptive method for at least the previous 3 months, see Section [5.1.1](#)
3. Age 18-70 years, inclusive
4. Body Mass Index (BMI) 18.5 – 35.0 kg/m², inclusive
5. Have at least 6 months history of GERD symptoms (need not to be consecutive)
6. Continuously treated during the last 4 weeks before enrolment with daily optimized unchanged PPI therapy with doses according to the country label, or regional where applicable, for any GERD indication. Patients with endoscopy verified reflux esophagitis (Los Angeles classification grade A-D) within the last 8 weeks must have completed the prescribed 8 weeks treatment with a PPI. An optimized PPI treatment is a treatment which according to the investigator judgment can not be further improved by changing brand or dosing of the PPI.

7. Have a PPI prescription with refills that cover the whole study period or instructions by a physician to use an over the counter (OTC) PPI in accordance with the labelling of their prescription counter-part
8. Able to read and write in the local language and use the e-diary device
9. **To be eligible for the screening phase** the patients must have reported in the RESQ-7 using 7 days recall of symptoms, a minimum of 3 days and a rating of at least moderate intensity on at least one of the following items; a burning feeling behind the breastbone or unpleasant movement of material upwards from the stomach. (An algorithm which is programmed in the e-diary device, will determine eligibility automatically).
10. **To be eligible for randomization** the patients must have recorded in the RESQ-eD on the last 7 days before randomization, a minimum of 3 days with a symptom intensity of at least moderate on either item, or any combination of both items (eg 1 day on one item and 2 days on the other); a burning feeling behind the breastbone or unpleasant movement of material upwards from the stomach. (An algorithm, which is programmed in the e-diary device, based on the e-diary recordings, will determine whether the patient fulfils the criteria).
11. An upper gastrointestinal endoscopy is required before randomization provided that:
 - no endoscopy has been performed within the past 24 months

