The proportion of days of not more than mild symptoms with respect to a domain during a specified time period will be calculated as: the number of days when none of the items in the domain has a daily intensity that exceeds “Mild” (numerical value 2) divided by the number of expected values in the specified time period. That is, a day with missing value will be regarded as a day with more than mild symptoms.

Baseline will be defined as the seven days prior to visit 2 (Randomization visit). Hence, the last e-diary registration that contributes to the baseline period will be the morning registration on the day of visit 2.

A patient’s treatment period will be defined as the days from the day of first dose up to and including the day of last dose. Hence, the first e-diary registration contributing to the treatment period will be the evening registration on the day of the first dose, and the last e-diary registration contributing to the treatment period will be the morning registration on the day of the last dose. If the date of the first dose has not been entered in the database, the date of the first dose will be imputed to the date of visit 2 (Randomization visit). If the date of the last dose has not been entered in the database, the date of the last dose will be imputed to the date of visit 6 (End of treatment visit).

The change from baseline to the treatment period in proportion of days of not more than mild symptoms with respect to a domain will be calculated as the proportion of days of not more than mild symptoms with respect to the domain during the patient’s treatment period minus the proportion of days of not more than mild symptoms with respect to the domain during the patient’s baseline period.

Primary outcome variable:

A responder is defined as a patient who experiences at least three more days of not more than mild symptoms on average per week during treatment compared to baseline, based on the Overall symptoms domain in the RESQ-eD. This means that the increase from baseline to the treatment period in the proportion of days of not more than mild symptoms will exceed or equal 3/7 for a responder. A patient that is not classified as a responder according to this criteria will be classified as a non-responder. The primary outcome variable is the binary variable (yes/no) indicating a patient who meets the responder definition.

Secondary outcome variables:

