An alternative definition of a responder is a patient who experiences at least five days of not more than mild symptoms on average per week during treatment, based on the Overall symptoms domain in the RESQ-eD. This means that the proportion of days of not more than mild symptoms during the treatment period will exceed or equal 5/7 for a responder. A patient that is not classified as a responder according to these criteria will be classified as a non-responder. A secondary outcome variable is the binary variable (yes/no) indicating a patient who meets the alternative responder definition.

The change from baseline to the treatment period in proportion of days of not more than mild symptoms, as defined above, with respect to the Overall symptoms domain, the Heartburn domain, the Regurgitation domain, the Hoarseness, cough, difficulty swallowing domain and the Burping domain will be analysed as secondary outcome variables.

For the assessment of basic measurement properties of the RESQ-eD the following variables will be derived:

- Item intensity over baseline will be derived as the mean of the daily item intensities during the seven days that form the baseline period.
- Domain intensity over baseline will be derived as the mean of the daily domain intensities during the seven days that form the baseline period. If more than two daily domain intensity values are missing during the seven day period for a patient, the baseline intensity will be set to missing.
- Domain intensity over the seven days prior to visit 4 will be derived as the mean of the daily domain intensities during the seven days. The last e-diary registration that contributes to the seven day period will be the morning registration on the day of visit 4. If more than two daily domain intensity values are missing during the seven day period for a patient, the intensity for the seven days prior to visit 4 will be set to missing.
- Domain intensity over the treatment period will be derived as the mean of the daily domain intensities during the treatment period. If the patient has less than 7 days on treatment or if more than 30% of the daily domain intensity values

during treatment are missing then the domain intensity over the treatment period will be set to missing.

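### The plot planned in 12.2.3.8 to check both responder definitions is on the change scale, so it shows the alternative cut-off (5/7 on treatment) directly only for patients with a baseline of 0/7

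*Protocol*

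**What the plan says.** Section 12.2.3.8 sets out to evaluate the values behind two definitions: "both the responder definition and the alternative responder definition originally derived in study". The study meant is the earlier validation study, D9120C00027. One display is named for the pair. They "will be evaluated by graphical depiction of the intra-patient change in proportion of days of not more than mild symptoms from baseline". The other axis is cumulative: the share of each OTE group that reaches a given change. Four collapsed groups are shown (no change and three grades of improvement), with the OTE taken at visit 6 or on stopping early.

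Section 11.3.1 defines the two variables on different scales. A primary responder is one for whom "the increase from baseline to the treatment period in the proportion of days of not more than mild symptoms will exceed or equal 3/7". The alternative is worded as a level: "the proportion of days of not more than mild symptoms during the treatment period will exceed or equal 5/7 for a responder"; baseline does not enter.

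Criterion 10 in section 4.1 looks at the week leading up to randomization and requires "a minimum of 3 days with a symptom intensity of at least moderate on either item, or any combination of both items". The two items are burning behind the breastbone and unpleasant upward movement of material from the stomach.

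No other section plans the on-treatment proportion by OTE category. Section 12.2.3.4 plots patients by day without the OTE. Section 12.2.3.7 uses the OTE categories, but with effect sizes on domain intensity.

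**The concern.** A cut-off on a level can be read from a change axis only if every patient has the same baseline. The entry rule does not fix the baseline, and section 12.2.2 adjusts the primary model for it because baseline symptom frequency is expected to be associated with response. Section 12.2.3.8 therefore promises an evaluation of the 5/7 cut-off that its own display does not deliver directly.

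At stake is how well the 5/7 value is supported by patients' own ratings of change in this study. The alternative definition is the first-listed secondary objective (section 2.2) and has odds ratios for each dose (section 12.2.3.1), so readers will want to know whether its cut-off separates the OTE categories. Section 12.2.3.8 implies that they will be shown this.

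**Working it through.** The protocol gives no numerical result for this check, so there is none to reproduce. Its conversions of 3 and 5 days per week to 3/7 and 5/7 are right. Below, a good day is one on which no Overall item exceeds mild.

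**Step 1: range of baselines.** Both entry items belong to the Overall domain (section 11.3.1). A day with either at moderate (3, above the limit of 2) is not a good day. Missing days count as not good, and imputing a missing rating cannot lower an observed one. With a seven-day baseline and at least 3 such days, good days number at most 7 − 3 = 4. So baseline b lies in {0, 1, 2, 3, 4}/7.

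**Step 2: change needed.** On-treatment level = b + change. The alternative definition holds if b + change ≥ 5/7, that is, change ≥ 5/7 − b. The primary definition holds if change ≥ 3/7.

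The last two columns assume, for illustration, 28 evaluable treatment days: primary needs 28 × (b + 3/7) good days, alternative needs 28 × 5/7 = 20.

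| Baseline b | Change needed for alternative | Alternative met at a change of exactly 3/7? | Good days in 28 for primary | Good days in 28 for alternative |
|---|---|---|---|---|
| 0/7 | 5/7 | no (level 3/7) | 12 | 20 |
| 1/7 | 4/7 | no (level 4/7) | 16 | 20 |
| 2/7 | 3/7 | yes (level 5/7) | 20 | 20 |
| 3/7 | 2/7 | yes (level 6/7) | 24 | 20 |
| 4/7 | 1/7 | yes (level 7/7) | 28 | 20 |

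The definitions coincide only at b = 2/7. From lower baselines a patient can meet the primary but not the alternative definition (12 to 19 good days at 0/7; 16 to 19 at 1/7). From higher baselines the reverse is possible (20 to 23 good days at 3/7; 20 to 27 at 4/7).

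**Step 3: what the planned curve can say about 5/7.**
- Change ≥ 5/7: level ≥ 0 + 5/7, so the alternative definition is always met.
- Change < 1/7: level < 4/7 + 1/7 = 5/7, so it is never met.
- Change from 1/7 up to but not including 5/7: the answer depends on baseline, which the plot does not show.

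Let G(c) be the proportion of an OTE category with change ≥ c. Then G(5/7) ≤ proportion meeting the alternative definition ≤ G(1/7). The gap between the bounds is the proportion of patients with a change in the middle band, which contains the primary cut-off of 3/7. At b = 0/7, change and level are the same number and the curve can be read at 5/7 exactly.

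**The case against.** The strongest reply is that the mismatch may matter little in practice. A good Overall day requires all 13 items to be no worse than mild, each scored as the worse of the evening and morning ratings, with missing days counted as bad. Entry looks at only two of those items. Overall baselines may therefore sit well below the permitted maximum of 4/7, and the closer they are to 0/7, the closer change comes to level. This stands as a limit on size. It does not remove the point: the protocol gives no baseline distribution, and its own covariate adjustment implies some spread.

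It can also be said that this is a supportive display with no test, threshold or decision rule; that section 3.2 treats both definitions as already established in the validation study; that section 6.5.2 speaks of confirming one responder definition on the basis of change; and that an SAP, due before unblinding, could add a figure. All of this is fair and keeps the point modest. But section 12.2.3.8 does not leave the method open: it names the change plot and assigns it to both definitions.

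Stronger readings that a reader might infer are not supported:
- That the plot gives no evidence on 5/7. The bounds in step 3 show otherwise.
- That the 5/7 cut-off is being validated here for phase III. Section 12.2.3.8 states no such purpose; section 1.3 links phase III to dose selection.
- That +5/7 on the change axis will be mistaken for the alternative definition. The synopsis and sections 2.2 and 11.3.1 all state it plainly as an on-treatment level.
- That leaving out the deteriorated category is an error. For a cut-off of meaningful improvement, unchanged patients are a reasonable reference, and section 12.2.3.7 uses the full set of collapsed categories. Showing the fifth category is a preference.

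**Conclusion.** The point holds as an inconsistency of scale between section 12.2.3.8 and the alternative definition in section 11.3.1. The stated display evaluates the 3/7 change directly. It shows the 5/7 level directly only for patients with baseline 0/7, and otherwise only bounds it between the curve values at 5/7 and 1/7. How wide those bounds would be cannot be determined from the protocol.

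The conclusion assumes that the plot uses the Overall domain, on which both definitions rest, and that randomized patients satisfy criterion 10, so that baseline does not exceed 4/7.

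The effect is limited to one descriptive check of the instrument under a secondary objective. The primary logistic regression, the sample size and the pairwise comparisons on the alternative responder variable do not depend on it. It is worth correcting because a stated evaluation does not follow from the stated method and the remedy is nearly free.

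**What to change.** In section 12.2.3.8, tie each definition to a display on its own scale. Keep the cumulative plot of within-patient change for the primary definition, read at 3/7. Add a cumulative plot of the on-treatment proportion of good days in the Overall domain, by the same collapsed OTE categories and over the same treatment period, read at 5/7.

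The cost is one extra figure and a sentence of text, settled before unblinding. The on-treatment proportion is already derived under section 11.3.1 and the OTE is already collected, so no new data or visits are needed.

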12.2.3.9 Pharmacokinetic evaluation

A population PK evaluation will be made to fit a pharmacokinetic model to plasma concentration versus time data, and tables and graphs will describe PK analyses. The influence of patient covariates such as gender, age, body weight and creatinine clearance on the pharmacokinetic parameters will be explored. The AUC of plasma concentration will be correlated to proportion of days of not more than mild symptoms per dose level, to be able to analyse the relationship between the systemic exposure and the response.

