2.2 Secondary objectives

The secondary objectives of the study are:

- To evaluate the effect on GERD symptoms of four doses of AZD3355 (60 mg, 120 mg, 180 mg and 240 mg bid) compared to placebo, as add-on treatment to a PPI by using an alternative responder definition; ie, at least 5 days of not more than mild GERD symptoms on average per week during the whole treatment period based on the Overall symptoms domain in the RESQ-eD
- To evaluate the effect on GERD symptoms of four doses of AZD3355 (60 mg, 120 mg, 180 mg and 240 mg bid) compared to placebo, as add-on treatment to a PPI by analysing the change in the proportion of days of not more than mild GERD symptoms compared to baseline, based on the Overall symptoms domain and for

each separate domain (Heartburn; Regurgitation; Hoarseness, cough and difficulty swallowing; Burping) in the RESQ-eD

- To evaluate the dose-response curve with respect to:
 - The responder definition
 - The change in the proportion of days of not more than mild GERD symptoms compared to baseline, based on the Overall symptoms domain in the RESQ-eD
- To assess basic measurement properties of the RESQ-eD
- To assess the pharmacokinetics of AZD3355 by population PK analyses with special regard to variability in the patient population
- To study the relationship between systemic exposure and response with special regard to the responder definition
- To study the prevalence of mucosal breaks in the target population through endoscopy at baseline during the study or historical reports
- To describe the endoscopic findings after the study treatment period, in patients with baseline endoscopy showing mucosal breaks.

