3.1 Overall study design and flow chart

This is a randomized, double blind, placebo-controlled, parallel group designed, multi-centre phase IIb dose finding study to assess the effect on GERD symptoms, safety and tolerability during 4 weeks of treatment with four doses of AZD3355 as add-on treatment to a PPI. The target patient population in this study are partial responders to PPI treatment who experience

at least moderate intensity of GERD symptoms on at least 3 of the past 7 days despite optimised PPI treatment and must have a history of GERD symptoms for at least 6 months.

The effect evaluation will be based on patient reported symptom data, using twice-daily recordings in a hand-held electronic diary (e-diary) device using the RESQ-eD, (see Section 6.5).

The study consists of a screening phase, a treatment phase and a follow-up phase. The patients will be randomized to one of four doses of AZD3355 (60 mg, 120 mg, 180 mg or 240 mg bid) or matching placebo as add-on treatment to their optimized PPI treatment during 4 weeks, see Figure 1.

Approximately 650 patients from Canada, France, Germany, Hungary, Latvia, Romania and USA will be randomized in the study and approximately 130 sites will participate. The aim is to have an equal number of randomized patients in the five treatment arms.

Visit 1 (Enrolment visit)

At the enrolment visit 8-26 days before randomization after written informed consent is given, patients will receive brief training in how to use an e-diary device for completion of PRO assessments and will complete the screening questionnaire Reflux Symptom Questionnaire 7 day recall (RESQ-7), using the e-diary device, prior to any further assessment.

Each patient who fulfils the RESQ-7 eligibility criteria, which automatically is determined from an algorithm in the e-diary device, will continue with visit 1 screening procedures. The patients will then undergo a physical examination including weight and height, dECG, orthostatic test and a full laboratory screen. Women of childbearing potential will undergo a urine pregnancy test and will be asked to verify that they are using one of the accepted methods of contraception to be allowed to participate in the study.

Information regarding medical and surgical history and PPI usage will be collected. The patients will then be reevaluated for all inclusion and exclusion criteria. If not eligible for the study a minimum of required modules must be entered in the eCRF, see Section 5.9.

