11.4 Calculation or derivation of pharmacokinetic variables

The PK analyses will be performed at AstraZeneca R&D. Population mean and variability parameters will be estimated for oral total plasma clearance (CL/F), which determines total drug exposure, AUC, and for other pharmacokinetic parameters as applicable.

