12.2.2 Primary objective

The primary objective, to evaluate the effect of four doses of AZD3355 compared to placebo using the responder definition, will be evaluated by pairwise comparisons. Each dose level will be compared to placebo using logistic regression with dose as a factor variable. Based on experience from previous studies ([D9120C00011](#) and [D9120C00027](#)), the symptom frequency during baseline is expected to be associated with the response variable. Therefore, the proportion of days of not more than mild symptoms during baseline will be included as a covariate. The tests will be one-sided with a significance level of 10%. The multiplicity issue will be handled by using a step down procedure where AZD3355 is tested sequentially

starting with the highest dose. If the null hypothesis of no difference between AZD3355 240 mg and placebo is not rejected no further dose level will be tested. If the null hypothesis is rejected, AZD3355 240 mg is demonstrated to have an effect and AZD3355 180 mg will be tested compared to placebo. If the null hypothesis of no difference between AZD3355 180 mg and placebo is not rejected, no further dose level is tested. If the null hypothesis is rejected, AZD3355 180 mg is demonstrated to have effect and AZD3355 120 mg will be tested versus placebo.

Estimates and two-sided 95% confidence intervals of the odds ratios of each dose level compared to placebo will be calculated.

An additional explorative logistic regression with additional covariates will be fitted to the data. Details of this analysis will be presented in the SAP.

In addition, the proportion of responders per treatment will be presented.

Since the number of patients at each centre is expected to be few, the country-treatment interaction will be evaluated instead of centre-treatment interaction. A Breslow-Day's test (two-sided with a significance level of 10%) will be used to evaluate the country-treatment interactions for the primary variable.

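### The exposure-response analysis relates AUC to the raw on-treatment proportion of days, apparently within dose, although its objective singles out the responder definition

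*Protocol*

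**What the plan says.** Protocol section 2.2 (and the synopsis) lists as a secondary objective: "To study the relationship between systemic exposure and response with special regard to the responder definition".

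Section 12.2.3.9 describes one analysis for it: "The AUC of plasma concentration will be correlated to proportion of days of not more than mild symptoms per dose level". The same section says of the population PK model: "The influence of patient covariates such as gender, age, body weight and creatinine clearance on the pharmacokinetic parameters will be explored".

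Section 11.3.1 defines a responder as a patient for whom "the increase from baseline to the treatment period in the proportion of days of not more than mild symptoms will exceed or equal 3/7". It defines the proportion of days in a period, the change in that proportion, and responder status as three separate quantities.

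In the primary analysis (section 12.2.2), "the proportion of days of not more than mild symptoms during baseline will be included as a covariate", because baseline symptom frequency is expected to be associated with response.

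Patients are "randomized to one of four doses of AZD3355 (60 mg, 120 mg, 180 mg or 240 mg bid) or matching placebo" (section 3.1). Section 12.2.3.3 models response across nominal dose: a logistic regression for the responder variable, and an E-max model for the change in proportion of days.

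**The concern.** Two things do not fit together.

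First, the objective points to the responder definition, but the analysis sentence names another variable. Responder status depends on baseline as well as on the treatment period, so a correlation with the on-treatment proportion alone does not address it.

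Second, a correlation computed separately at each dose leaves out the AUC differences that randomization creates between doses and against placebo. What remains is AUC variation among patients on the same dose. Nobody randomizes that variation, and patient factors that bear on symptoms may also bear on it.

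Section 1.3 lists the exposure-response work next to the population PK work that is meant to inform the choice of dosing regimen. A correlation over a narrow exposure range could miss a real relationship. A confounded one could suggest a relationship that is not there.

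**Working it through.** **Plan's own figure.** The protocol gives no power or precision for the exposure-response analysis. Its only efficacy power figure (section 12.3) is about 90% for 24% against 39%, 130 per arm, one-sided 10%. It reproduces: z = (0.15·√130 − 1.2816·√(2·0.315·0.685)) / √(0.24·0.76 + 0.39·0.61) = (1.710 − 0.842)/0.648 = 1.34, power 91.0%. It does not bear on this point.

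**Step 1: can the stated variable stand in for responder status?** Take two patients whose baselines are both compatible with the randomization criterion in section 4.1 (at least 3 of 7 days with at least moderate symptoms).

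| Patient | Baseline | On treatment | Change | Responder (≥ 3/7)? |
|---|---|---|---|---|
| A | 0/7 | 4/7 | 4/7 | Yes |
| B | 3/7 | 5/7 | 2/7 | No |

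B has the higher on-treatment proportion and is the non-responder. The variable in section 12.2.3.9 can therefore order patients the opposite way from responder status, and it cannot recover that status without baseline. This step needs no assumption.

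**Step 2: what varies within a dose?** Section 11.4 refers to "oral total plasma clearance (CL/F), which determines total drug exposure, AUC". At a fixed dose AUC therefore varies only through CL/F, which is not randomized.

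**Step 3: how much slope information lies between doses?** From the protocol: doses 0, 60, 120, 180 and 240 mg, 130 patients per arm. Assumed: mean AUC proportional to dose, constant between-patient CV, effect linear in AUC, equal residual variance. Information on the slope is then proportional to the sum of squares of AUC. In units of 60 mg, dose is d = 0, 1, 2, 3, 4.

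- Within dose, active arms combined: 130·CV²·(1 + 4 + 9 + 16) = 3900·CV².
- Between doses, four active arms: 130·Σ(d − 2.5)² = 130·5 = 650.
- Between arms, placebo included: 130·Σ(d − 2)² = 130·10 = 1300.
- Pooled/within ratio, active arms: 1 + 650/(3900·CV²) = 1 + 1/(6·CV²).
- Pooled/within ratio, five arms: 1 + 1300/(3900·CV²) = 1 + 1/(3·CV²).

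| Assumed CV | Active doses | SE ratio (square root) | With placebo | SE ratio |
|---|---|---|---|---|
| 25% | 3.7 | 1.9 | 6.3 | 2.5 |
| 35% | 2.4 | 1.5 | 3.7 | 1.9 |
| 50% | 1.7 | 1.3 | 2.3 | 1.5 |

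**Step 4: check on the log scale, active arms only.** The variance of log dose over 60, 120, 180 and 240 is 0.271, and the within-dose variance of log AUC is log(1 + CV²). The between-dose share is 0.271/(0.271 + 0.0392) = 87% at CV 20% and 0.271/(0.271 + 0.3075) = 47% at CV 60%. A simulation (3,000 runs) assumed a 15-point rise in proportion of days from 60 to 240 mg, linear in log AUC, with residual SD 0.35. A correlation at a single dose was positive and significant (two-sided 5%) in 10% of runs at CV 20%, rising to 50% at CV 60%. The correlation pooled over the four doses was significant in 98% to 100%.

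**Step 5: does pooling cure confounding?** No. With no true effect and a spurious within-dose correlation of about 0.20, a single dose was significant in about 62% of runs. The pooled correlation shrank to 0.07 (CV 20%) to 0.14 (CV 60%), but with 520 patients it was still significant in 36% to 91% of runs. Any replacement model therefore needs the covariates that affect CL/F, not only baseline.

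**The case against.** The strongest reply has five parts.

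- **The randomized contrast is not lost to the trial.** A reader might infer that the plan leaves the randomized exposure differences unused. It does not: section 12.2.3.3 models response across dose and section 12.2.2 compares each dose with placebo. Because dose drives much of AUC, a pooled AUC model would partly repeat that work, and a within-dose look is a legitimate complement. This stands. The loss is confined to the exposure-response objective, since those analyses use nominal dose and not AUC.
- **The phrase about dose level may only mean display by dose, or response taken by dose.** Either reading would keep the between-dose contrast. This is possible, so the second limb rests on the ordinary reading. The first limb does not depend on it.
- **The objective is partly met.** It concerns exposure and response generally, and the proportion of days underlies the responder variable. True, but the part the objective singles out has no analysis.
- **Confounding is not shown.** A reader might infer that the within-dose correlation is confounded by weight, age or renal function. The protocol says only that their influence on PK parameters will be explored. It does not say that they alter AUC materially or predict symptoms. Confounding is a possibility and no more.
- **The statistical analysis plan can settle it.** Sections 12.2.2 and 12.2.3.3 expressly leave detail to that plan. Section 12.2.3.9 does not; it fixes outcome, method and grouping. What is at issue is what it states.

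**Conclusion.** The point holds. The mismatch between the objective and the stated variable is firm and rests on the text alone: no analysis of AUC against responder status is described, and the stated variable carries no baseline adjustment. The dose-level limb holds on the ordinary reading of the sentence.

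Its size is about 1.7 to 3.7 times the slope information when active doses are pooled, and 2.3 to 6.3 times with placebo at AUC = 0. These figures depend on an assumed CV of 25% to 50%, dose-proportional AUC and a linear effect. The linearity assumption is the more demanding with placebo included, given that section 12.2.3.3 itself plans an E-max curve. Ratios against one dose alone can be made much larger by choosing the lowest dose and the smallest CV; they are extremes and not a fair measure of the loss.

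This is an untested secondary objective. The primary test, the sample size and the dose-response curves are unaffected. The sentence should be changed because following it as written leaves the responder part of the objective without an analysis.

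**What to change.** Replace the correlation sentence in section 12.2.3.9 by:

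- a logistic regression of responder status on individual model-predicted AUC across all arms, with placebo at AUC = 0, adjusted for the baseline proportion of days and for covariates found to affect CL/F;
- the analogous model for change in the proportion of days, allowing a non-linear form such as E-max, in line with section 12.2.3.3;
- within-dose correlations or plots, labelled as a supportive check. A within-dose slope that disagrees clearly with the pooled one would be a warning of confounding.

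Covariate adjustment deals only with measured factors, so the AUC slope should still be read with the randomized dose-response curve beside it.

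The cost is one reworded passage and slightly more analysis work. No new data collection is needed: the diary already supplies baseline and response, and section 6.6.1 has PK samples taken from all patients. Samples are scheduled only at the week 2 and week 4 visits, so the wording should say how AUC is assigned to patients who stop before the first of these.
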